10.9.2 Study Completed

At the completion of the 30 (+7) day follow-up visit, non-oncologic subjects will be exited from the study. At the completion of the 5-year follow-up visit, oncologic subjects will be exited from the study. The 30 (+7) day or the 5-year follow-up visit and exit visit should be combined, and either the 30 (+7) or the 5-year follow-up eCRF and the Study Exit eCRF need to be completed.

10.9.3 Lost to Follow-up

A subject is considered to be lost to follow-up if the conditions in **section 10.9** are met. The method of attempt must be documented in the subject's medical record. In addition, regulation set forth by the governing IRB must be followed.

When subjects are lost to follow-up the Investigator will make efforts to confirm the vital status of the subject, as described in the informed consent.

10.9.4 Subject Chooses to Exit (i.e., Revokes Consent)

A subject can withdraw from the study at any time. If the subject wishes to exit from the study (i.e., the subject revokes consent), the study site is required to document the reason for exit on the Study Exit eCRF. In addition, study sites shall follow the regulations set forth by the governing IRB. If possible, the following data should be collected prior to subject withdrawal:

- Reason for exit

10.9.5 Investigator Withdraws Subject

No subjects should be withdrawn by Investigators unless compelling medical justification is present. It is recommended investigators discuss any withdrawals with the study team prior to withdrawing subjects. If an Investigator withdrawal is necessary, the following data should be collected prior to subject withdrawal if possible:

- Reason for subject withdrawal

10.9.6 Conditional Disengagement

After a subject is enrolled every effort should be made to keep the subject in the study. However, it is recognized that there are circumstances where limited data may be collected, or study exit will need to occur. In these cases, we will consider either modified data collection requirements where subjects may conditionally disengage in study procedures but data from the subject can still be collected because the subject has not revoked consent or exit when study participation is completely ended. Modified data collection is always preferred over exit.

Subjects may be conditionally disengaged from study procedures for any of the following reasons:

- Subject chooses to disengage (e.g., follow-up schedule cannot be adhered to, study burden too large, relocation to another geographic location but telephone follow-up still acceptable)
- Investigator deems conditional disengagement necessary (e.g., medically justified)

If the subject wishes to disengage from the study, or the Investigator deems it necessary, the study site is required to document the reason. Data collection requirements no longer apply, but study sites are encouraged to collect as much data as possible on the regular eCRFs.

11. Risks and Benefits

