9.2 Subject Enrollment

A subject is considered enrolled in the study when the consent process is signed and dated. Screening data will not be collected for the study until the subject has been determined to be eligible for the study and signed consent (see **Section 10.2** for details). If the subject is consented prior to the day of surgery, a re-verification of eligibility will be signed off by the PI or Sub-I on the day of surgery. As soon as the surgical procedure has begun with the Medtronic Hugo™ RAS System, the subject must be followed

Medtronic Business Restricted

This document is electronically controlled

CONFIDENTIAL 056-F275 Rev E Clinical Investigation Plan Template

regardless of whether or not the subject completed the surgical procedure with the Medtronic Hugo™ RAS System. Subject enrollment will be consecutive at the institution according to required procedure types and eligibility criteria. See **Section 9.3** for additional details.

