10.1.5 Post-Operative Follow-Up Visits (Visit 4-8)

Post-operative visits 4-8 for oncologic subjects will be made via a phone call to assess overall survival, progression-free survival, and disease-free survival.

Medtronic Expand URO Clinical Investigation Plan

MDT19051EINURO

Version 9.0

Page 40 of 111

Medtronic

Table 6. Data Collection and Study Procedure Requirements at Subject Visits

Procedure/Assessment	Screening (Day -30 to 0) Visit 1	Surgical Procedure (Day 0) Visit 2	Hospital Discharge Visit 2.1	Follow-Up (30+7 Days) Visit 3	Follow-up (Years 1 - 5) (+/- 3 mo. window) Visits 4-8
	May be Combined				
Informed Consent Form ¹	X	X			
Eligibility Criteria	X	X			
Demographic Data	X				
Medical/Surgical History	X				
Concomitant Medication(s)	X	X	X	X	
Lab Values (if applicable)	X	X	X	X	
Robot Setup Time		X			
Total Operative Time (skin to skin)		X			
Surgeon Console Time		X			
Instruments Used		X			
Estimated Blood Loss		X			
Transfusion ³		X	X	X	
Conversion to a robotic-assisted approach utilizing an FDA cleared robotic-assisted device, open or manual laparoscopy		X			
Robot Take Down Time		X			
Warm Ischemia Time (if applicable)		X			
Anastomotic Leak Test performed (if applicable)		X			
Anastomotic Stricture (if applicable)		X			
Rate of Positive Circumferential Margins on Final Pathology (if applicable)		X			
Margin (mm) (if applicable)			X		

Medtronic Business Restricted

This document is electronically controlled

CONFIDENTIAL 056-F275 Rev E Clinical Investigation Plan Template

Medtronic Expand URO Clinical Investigation Plan

MDT19051EINURO

Version 9.0

Page 41 of 111

Medtronic

Procedure/Assessment	Screening (Day -30 to 0) Visit 1	Surgical Procedure (Day 0) Visit 2	Hospital Discharge Visit 2.1	Follow-Up (30+7 Days) Visit 3	Follow-up (Years 1 - 5) (+/- 3 mo. window) Visits 4-8
Tumor Size (if applicable)			X		
Tumor Stage (if applicable)			X		
Total number of lymph nodes retrieved			X		
Catheterization Time			X	X	
Mortality			X	X	X
Length of Hospital Stay			X		
Reoperation			X	X	X
Pain Medication			X	X	
Medications if associated with an AE	X	X	X	X	X
Adverse Events ²	X	X	X	X	X
Readmission				X	X
Device Accountability		X			
Device Deficiency		X			
Protocol Deviation Collection (if applicable)	X	X	X	X	X
Study Exit				X	X

¹Study specific procedures may only be performed after subject has agreed to participate and signed the informed consent form.

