10.8 Deviation Handling

A study deviation is defined as an event within a study that did not occur according to the CIP or the CTA.

Prior approval by Medtronic is expected in situations where the Investigator anticipates, contemplates, or makes a conscious decision to deviate. Prior approval is not required when a deviation is necessary to protect the safety, rights, or well-being of a subject in an emergency or in unforeseen situations beyond the Investigator's control (e.g., subject failure to attend scheduled follow-up visits, inadvertent loss of data due to computer malfunction, inability to perform required procedures due to subject illness).

For medically justifiable conditions which preempt a subject's ability to complete a study-required procedure, it may be permitted to report only one deviation which will apply to all visits going forward. This may also apply for other unforeseen situations (e.g., the subject permanently refuses to complete a study required procedure and the data will not contribute to the primary end point analysis). However, prior approval from Medtronic is required for such situations.

All study deviations must be reported on the CRF regardless of whether medically justifiable, pre-approved by Medtronic, an inadvertent occurrence, or taken to protect the subject in an emergency. Multiple deviations of the same type at the same visit may be reported on one case report form.

In the event the deviation involves a failure to obtain a subject's consent or is made to protect the life or physical well-being of a subject in an emergency, the deviation must be reported to the IRB as well as Medtronic within five (5) working days. Reporting of all other study deviations should comply with IRB policies and/or local laws and must be reported to Medtronic as soon as possible upon the study site becoming aware of the deviation. Reporting of deviations must comply with IRB policies, local laws, and/or RA requirements.

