10.9.1 Study Exit

A study exit eCRF is required for all subjects. Prior to exiting a subject from the study, it is recommended

to follow the subject until all ongoing system and/or procedure related AEs are resolved or unresolved with no further actions planned.

Following exit, subjects will continue to receive standard medical care. Upon exiting from the study, no further study data will be collected, or study visits will occur for the subject. All data available through the time of the subject's exit will be used for analysis.

Subjects are urged to remain in the study as long as possible but may be exited from the study for any of the following situations:

- Study completed
- Subject lost to follow-up
- Subject death
- Subject did not meet inclusion/exclusion criteria
- Subject did not provide consent (or data use protection authorization)
- Subject chooses to withdraw (e.g., consent withdrawal, relocation to another geographic location)
- Investigator deems withdrawal necessary (e.g., medically justified, inclusion/exclusion criteria not met, failure of subject to maintain adequate study compliance)

The following information is required to be collected at study exit:

- Reason for exit

If discontinuation is because of safety or lack of effectiveness, the subject shall be asked to be followed for collecting safety data outside the clinical investigation.

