12.1 Adverse Events

All Adverse Events (AEs) will be collected, starting from the time the informed consent form is signed through 30 days (+7) after the day of the procedure regardless of their severity or relationship to the Hugo™ RAS or study procedures. After 30 days, AEs will be assessed by the surgeon and those AEs deemed attributable to the underlying surgical indication, procedure or surgical device will be reported. All deaths will be collected via AE regardless of relatedness. Reporting of these events to Medtronic will occur on an AE Form, including event description, date of AE, treatment, resolution, assessment of both the seriousness of the AE and the relatedness to the system components. Each AE must be recorded on a separate AE eCRF.

AE definitions used in this study are based on ISO 14155:2020 (Clinical Investigation of Medical Devices for Human Subjects -- Good Clinical Practice). Documented pre-existing conditions are not considered AEs unless the nature or severity of the condition has worsened. See **Section 14.1** for details regarding AE analyses in each study analysis set. In addition, AEs impacting users or other persons (non-subject AEs) will be collected on a non-subject AE CRF.

Any unresolved procedural or device-related events that are still ongoing past study exit will be monitored by the physician per their institutional standard-of-care.

Unavoidable adverse events (UAE) (those that are inherent to the procedure and are expected to occur in all subjects for an expected duration) listed in **Table 9** will not be captured or reported unless the adverse event worsens or persists outside the stated timeframe post procedure. **Section 11.1** includes a list of several, but not an all-encompassing anticipated adverse events.

All deaths, serious adverse events related to the Hugo™ RAS System and/or study procedures and Clavien-Dindo Grade III and IV complications will be adjudicated by an independent CEC.

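### Protocol 10.9.6 lifts data collection requirements for conditionally disengaged subjects, in conflict with duties elsewhere, and the SAP does not say how a treated subject without 30-day status is counted for safety

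*Protocol*

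**What the plan says.** Protocol Section 10.9.6 creates a status between full participation and exit. The subject has not revoked consent, and the stated aim is to keep data: "Modified data collection is always preferred over exit". Two routes lead there: the subject's own choice, or "Investigator deems conditional disengagement necessary (e.g., medically justified"). The reason must be documented. The section then ends: "Data collection requirements no longer apply, but study sites are encouraged to collect as much data as possible on the regular eCRFs". It makes no exception for subjects already operated on, for the 30-day window, or for AEs and deaths.

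Other parts of the protocol are mandatory and do not mention disengagement:

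- Section 9.2: "As soon as the surgical procedure has begun with the Medtronic Hugo™ RAS System, the subject must be followed", whether or not the operation was completed with the device.
- Section 12.1: "All Adverse Events (AEs) will be collected, starting from the time the informed consent form is signed through 30 days (+7"), counted from the day of the procedure. Deaths are collected whatever their cause.
- Table 6, second footnote: AEs and SAEs are to be followed to resolution or study exit. A disengaged subject has not exited.
- Section 12.6: every death is to be reported to the sponsor.

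On the analysis side, SAP Section 7.4 uses the FAS without imputation. SAP 7.9.1.6 expressly drops subjects whose conversion endpoint is missing. The parallel safety section, 7.9.2.6, says only that FAS subjects are included. Multiple imputation of the safety endpoint starts above 5% missing (7.9.2.7), and SAP 7.12 rules out a tipping-point analysis for safety.

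**The concern.** The safety tests need to know, for every treated subject, whether a Grade III or higher complication occurred by day 30. Under SAP 7.9.2.2 that status is derived from AE records. A site that applies the last sentence of 10.9.6 as written may stop supplying those records while the subject remains in the study and in the FAS. With no AE form on file, a program that searches for qualifying events finds none, and the subject can be counted as event-free.

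One of the two routes is a medical decision by the investigator, so the loss may be related to outcome. The request for continued safety follow-up in Section 10.9.1 ("If discontinuation is because of safety or lack of effectiveness, the subject shall be asked to be followed for collecting safety data") is written for study exit and does not clearly reach a disengaged subject. Section 10.8 limits its refusal example to cases where "the subject permanently refuses to complete a study required procedure and the data will not contribute to the primary end point analysis"; Section 10.9.6 has no such limit.

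The long-term endpoints are touched as well. "Post-operative visits 4-8 for oncologic subjects will be made via a phone call", so the yearly survival and disease contact is light, yet 10.9.6 would make that optional too.

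**Working it through.** **1. Reproduce the plan's figures.** Inputs are from Protocol 14.4.2. The test is exact binomial: c is the largest count with P(X ≤ c | n, goal) ≤ α, and power is P(X ≤ c | n, expected rate).

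- Nephrectomy and prostatectomy, n=49, goal 0.20, α=0.008, expected rate 0.029: c=3, size 0.0067, power 0.947 (plan: 95%).
- Cystectomy, n=27, goal 0.45, α=0.008, expected rate 0.141: c=5, size 0.0038, power 0.829 (plan: 83%).

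Both reproduce. The 10% attrition allowance behind n=49 and n=27 protects power. It does nothing about bias from events that go unrecorded.

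**2. If unrecorded events count as no event.** Take full enrolment (n=55 and n=31), a true rate equal to the goal, and a share h of events unrecorded. The observed event probability is goal × (1 − h), for example 0.20 × 0.9 = 0.18 and 0.45 × 0.9 = 0.405. The false-pass probability is P(X ≤ c | n, goal × (1 − h)). The values of h are assumptions.

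| Cohort and Holm step | Pass if X ≤ | h=0 | h=5% | h=10% | h=20% |
|---|---|---|---|---|---|
| n=55, last step (0.025) | 5 | 2.45% | 3.7% | 5.3% | 10.7% |
| n=31, last step (0.025) | 8 | 2.3% | 4.0% | 6.6% | 16.0% |
| n=55, first step (0.025/3 = 0.83%) | 3 | 0.24% | 0.40% | 0.66% | 1.7% |
| n=31, first step (0.83%) | 6 | 0.27% | 0.55% | 1.09% | 3.6% |

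At the last step every non-zero loss shown exceeds the nominal level. At the first step the discreteness of the test absorbs 5% loss in both cohorts and 10% loss at n=55. It does not absorb 10% at n=31, or 20% in either.

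**3. If subjects without 30-day status are excluded.** Loss unrelated to outcome then leaves the test at or below its level. With two of 55 excluded, the last-step cut-off is 4 and P(X ≤ 4 | 53, 0.20) = 1.2%. With one of 31 excluded, it is 7 and P(X ≤ 7 | 30, 0.45) = 1.2%. Only loss related to outcome biases the rate under this handling.

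**4. The imputation trigger.** Counted by cohort, 5% of 55 is 2.75 and 5% of 31 is 1.55, so two subjects (3.6%) or one (3.2%) can lack status without triggering imputation. Counted over 141, 5% is 7.05, so seven can (7/141 = 4.96%). At the first Holm step, two hidden events turn a true count of 5 of 55 (fail) into 3 (pass), and one turns 7 of 31 (fail) into 6 (pass). No planned safety tipping-point analysis would show this.

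**The case against.** The strongest reply is that 10.9.6 should be read with the rest of the protocol. It disengages subjects from study procedures and says their data can still be collected. The AE, SAE and death duties in Sections 12.1, 12.5.2 and 12.6 and Table 6 make no exception for it. Section 9.2 is chiefly about keeping converted subjects in follow-up. This stands to the extent that a reader who infers that no data item at all is required any more goes too far: that holds only on a literal reading of one sentence. It does not remove the conflict, because neither set of passages refers to the other and a site can follow either.

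Several further points also stand:

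- Section 10.8 requires sponsor approval for a single going-forward deviation. This is a relevant control, though it does not name disengagement.
- A reader might infer that the loss would be invisible. The reason must already be documented, and Protocol 14.1 summarizes visit compliance, so a missed 30-day visit would show there.
- A reader might infer that relocation ends phone visits. The example in 10.9.6 describes phone contact that remains acceptable, so it is not a reason to delete relocation from the list.
- A reader might infer that medical justification means a poor outcome. The text allows that but does not say it.
- SAP 7.12 argues that missing safety data are unlikely because the endpoint would require hospitalization. This lowers the expected loss, but does not supply a rule for when it occurs.
- The calculation in step 2 treats all lost events as occurring after disengagement. In-hospital events recorded beforehand would not be lost.

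**Conclusion.** The contradiction is real and should be corrected. Section 10.9.6, taken at its word, makes 30-day primary safety data optional for consenting treated subjects, while four other places in the protocol keep follow-up, AE collection or death reporting mandatory. The SAP leaves open whether a FAS subject without 30-day status is counted as event-free or left out of the safety test.

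The size is conditional. The rise to 5.3% and 6.6% needs three things together: 10% of events lost, those events counted as absent, and the 0.025 level, which applies only after the other two null hypotheses have been rejected. That last step does matter if success requires all three surgery types to pass, because the largest p-value is then judged there. The stronger statement that lost events can only lower the tested rate is not supported: it is true if they are counted as no event, but under exclusion the effect depends on who is lost. Nothing in the documents says how many subjects will be disengaged, so the figures show sensitivity and do not forecast an error rate.

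**What to change.** Reconcile Protocol 9.2, 10.9.6 and 12.1 by replacing the last sentence of 10.9.6. For treated subjects who have not revoked consent, require these items by phone or record review:

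- through day 30: AEs with Clavien-Dindo grade, readmission, reoperation and vital status;
- for oncologic subjects: yearly vital and disease status.

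Record the date of disengagement beside the reason that is already required, and show these subjects in the disposition table. In SAP 7.9.2.6, state that a disengaged subject with no recorded event and incomplete 30-day follow-up is missing, not event-free, for the safety endpoint. A subject with a recorded event counts as an event whatever the later follow-up.

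The cost is protocol and SAP wording, one date field, and a few phone or chart contacts. Some subjects who disengage because of study burden might revoke consent instead; allowing record review in place of contact keeps that risk small.

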11.1 Potential Risks

Medtronic follows rigorous Quality Assurance and Control procedures throughout the life of a product, from the business analysis phase through development, market release, and post-market surveillance.

Medtronic Expand URO Clinical Investigation Plan

MDT19051EINURO

Version 9.0

Page 50 of 111

Medtronic

The Medtronic risk management process follows ISO 14971:2012, Medical Devices -- Application of Risk Management to Medical Devices and applicable requirements of YY/T 0316-2008 Medical devices—Application of risk management to medical devices (ISO 14971: 2007, IDT).

The Risk Management Report (RE00308824) summarizes the risk management activities for the Hugo™ RAS System as stated in the Risk Management Plan (R0057077), as well as the overall acceptability of risk. The Risk Management Report addresses risks resulting from the interaction between the user, the subject, and the device. It does not focus on risks inherent to medical treatment enabled by the Hugo™ RAS System. This risk analysis assumes that the product shall only be operated by qualified, properly trained medical personnel. While every attempt has been made to reduce subject and user risks, all surgeries using Hugo™ RAS System carry some residual risk, even when used by trained physicians.

Specific details of hazardous situations, causes, and risk control measures are identified in the Risk Analysis Chart (RE00027518). Hazardous situations as described in the Risk Management Plan, their associated harms, and specific device benefits to mitigate these hazardous situations are identified below.

- Arrhythmia
- Bleeding
- Blunt Trauma
- Bowel Perforation
- Burn (varying Degrees)
- Burn, Bowel
- Burn, Thermal
- Crushing Injury
- Damage to equipment/facility
- Delay of Treatment (Prolonged procedure)
- Electric Shock
- Foreign Body in Patient
- Implant, Failure of
- Infection
- Inflammation
- Tissue Damage/Tissue Trauma
- Toxicity
- Vessel Perforation

Medtronic Business Restricted

This document is electronically controlled

CONFIDENTIAL 056-F275 Rev E Clinical Investigation Plan Template

The incidence of these risks may be different than anticipated due to unknown circumstances or medical conditions.

There may be other discomforts and risks related to the Hugo™ RAS System and/or this study that are not foreseen at this time. In addition, the Hugo™ RAS System for urological indications is investigational in the United States and may be no more or less safe or effective than other commercially available robotic surgery systems.

The study sponsor may decide to stop the study before obtaining approval of the investigational product but will continue to guarantee subjects safety.

11.2 Risk Minimization

The potential risks associated with the Medtronic Hugo™ RAS System were identified and have been successfully mitigated in the risk management process described above. Medtronic has further minimized the possibility of risks by performing required laboratory and preclinical testing prior to this clinical study and implementing quality control measures into production processes.

Any potential risks associated with participation in this study are further minimized by providing guidelines for subject selection and evaluation, providing adequate instructions and labeling, selecting qualified investigators, and training study personnel on the safe use of the device and on the CIP procedures.

Medtronic has also attempted to minimize risk to subjects by using an independent Clinical Events Committee to review safety issues identified as part of the study.

The potential risks associated with the Medtronic Hugo™ RAS System have been identified above and will be constantly monitored, assessed, and documented by the Investigators and sponsor.

